7.1.3. Analyses for Time to Event Data

Time-to-event endpoints will be summarized using the Kaplan-Meier method. The median, quartiles, and probabilities of an event at particular time points will be estimated by the Kaplan-Meier method.

Confidence interval for the Kaplan-Meier estimation is calculated using the exponential Greenwood formula via log-log transformation of the survival function.

A stratified log-rank test will be used to compare relugolix+E2/NETA group to placebo group. Randomization stratification factors (pivotal study baseline MBL volume (<225 mL vs. 225 mL) and duration of exposure to relugolix (28 week vs. 52 weeks)) will be used for the stratified log-rank test..

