7.3.1.1. Kaplan-Meier Analysis

The primary endpoint of sustained responder rate at Week 76 will be estimated based on the Kaplan-Meier (KM) survival functions of time to 1st relapse (MBL volume ≥ 80 mL) along with 95% CI for sustained responder rate for each treatment group.

The 95% CI for the KM estimation of the sustained responder rate at Week 76 (Day 169) is calculated using the exponential Greenwood formula via log-log transformation of the survival function.

The 95% CI for treatment difference in sustained responder rates will be calculated via linear transformation of the difference in relapse free survival function with pooled variance, as follows:

$$[(\widehat{S}_R(t) - \widehat{S}_P(t)) - 1.96 \sqrt{\widehat{V}[\widehat{S}_R(t) - \widehat{S}_P(t)]}, (\widehat{S}_R(t) - \widehat{S}_P(t)) + 1.96 \sqrt{\widehat{V}[\widehat{S}_R(t) - \widehat{S}_P(t)]}].$$

Treatment difference in sustained responder rates at Week 76 between relugolix and placebo will be estimated along with 95% CI using the method described below.

Variance of treatment difference will be calculated using the formula:

$$\widehat{V}[\widehat{S}_R(t) - \widehat{S}_P(t)] = \widehat{V}[\widehat{S}_R(t)] + \widehat{V}[\widehat{S}_P(t)];$$

Where each of the variance of the KM estimate will be calculated using the Greenwood's formula

$$\hat{V}[\hat{S}(t)] = \hat{S}(t)^2 \sum_{t_i \leq t} \frac{d_i}{n_i(n_i - d_i)}$$

where n_i denotes the number of patients at risk at time t_i and d_i denotes the number of events observed at time t_i .

P-value for testing treatment difference in sustained responder rates at Week 76 between relugolix+E2/NETA and placebo will be derived using an appropriate test statistic, as described in the following steps.

Step A: The stratified test statistics via log-log transformation of the difference in survival curve at a fixed time point will be used to derive the -value (Klein et al. 2007).

$$x^2 = \frac{\left\{ \sum_{s=1}^M [\log(-\log(\widehat{S}_{R_s}(t))) - \log(-\log(\widehat{S}_{P_s}(t)))] \right\}^2}{\sum_{s=1}^M \left\{ \frac{V(\widehat{S}_{R_s}(t))}{[\widehat{S}_{R_s}(t) \log(\widehat{S}_{R_s}(t))]^2} + \frac{V(\widehat{S}_{P_s}(t))}{[\widehat{S}_{P_s}(t) \log(\widehat{S}_{P_s}(t))]^2} \right\}}$$

Where s is the s^{th} stratum in the total of M strata and $t = \text{Week 76 (Day 169)}$ in this case. Each stratified test statistics at a fixed time under two samples follows a chi-square distribution with one-degree freedom.

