Step B: If the stratified test statistics cannot be calculated due to event having not occurred in certain stratum, unstratified test will be used instead.

Step C: If unstratified test is still not estimable, the stratified version of the Mantel-Haenszel test using pooled KM estimators in each stratum will be constructed as the following. This test statistics follows a chi-square distribution with one-degree freedom.

$$\chi_{MH}^2 = \frac{\left\{ \sum_{s=1}^M \frac{n_{R_s} n_{P_s}}{n_{R_s} + n_{P_s}} (\widehat{S}_{R_s}(t) - \widehat{S}_{P_s}(t)) \right\}^2}{\sum_{s=1}^M n_{R_s} n_{P_s} V(\widehat{S}_{pooled_s}(t))}$$

It is noted that sustained responder rate at Week 104 (Day 365) as a key secondary endpoint will be defined as the KM estimates from the same KM curves and will be analyzed using the same method as described above.

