7.4.2.4. Time to Resumption of Menses

For time to resumption of menses among those who were amenorrheic at Week 52/Baseline, time-to-event will be defined as weeks from first dose of the Randomized Withdrawal study drug to first occurrence of the menses resumption during the randomized treatment period. Patients without an event will be censored at last assessment date prior to the last dose of randomized withdrawal study drug before Week 104.

Kaplan-Meier methods will be used to describe the time to event distributions by Week 76 and by Week 104 for each study treatment arm. Difference (95% CI) in the rate of menses resumption between the two treatment groups will be calculated at Week 76 and Week 104 based on the KM estimates. P-value from the unstratified log-rank test for treatment comparison in the KM rates at Week 76 and Week 104 will be provided. See Section 7.1.3 for more details.

7.4.2.5. Proportion of Patients with Menstrual Blood Volume \geq 80 mL at Any Timepoint During the 52-week Randomized Treatment Period

Proportion of patients with menstrual blood volume \geq 80 mL at any timepoint during the randomized treatment period will be summarized by visit based on the Kaplan-Meier estimates. The treatment differences (95% CI) in the proportions at Week 76 and at Week 104 will be provided using the analysis method described above in Section 7.4.1.1.

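### The p-value for the Week 76 and Week 104 menses-resumption rates comes from a log-rank test, which does not test those rates, and its lack of stratification is unexplained

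*SAP*

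**What the plan says.** SAP Table 1 lists two other-secondary endpoints on menses: the proportion of women whose menses resumed, and the time to resumption. Both are confined to women amenorrheic at Week 52/Baseline. Section 7.4.2.3.2 takes the estimates and intervals for the proportion from the Kaplan-Meier (KM) method of Section 7.4.2.4.

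Section 7.4.2.4 first plans two fixed-time contrasts: "Difference (95% CI) in the rate of menses resumption between the two treatment groups will be calculated at Week 76 and Week 104". The next sentence is: "P-value from the unstratified log-rank test for treatment comparison in the KM rates at Week 76 and Week 104 will be provided". The paragraph closes: "See Section 7.1.3 for more details".

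The related rules are:

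- **SAP 7.1.3, time-to-event data in general:** "A stratified log-rank test will be used to compare relugolix+E2/NETA group to placebo group". The factors are pivotal baseline menstrual blood loss (MBL, cut at 225 mL) and prior relugolix exposure (28 or 52 weeks), which gives four strata. No endpoint is excepted.
- **SAP 7.4.1.1, time to relapse:** the p-value comes from the stratified log-rank test.
- **SAP 7.3.1.1, KM rates at a fixed day:** "The stratified test statistics via log-log transformation of the difference in survival curve at a fixed time point will be used". An unstratified version is a fallback: "If the stratified test statistics cannot be calculated due to event having not occurred in certain stratum, unstratified test will be used instead". The same method serves Week 104 (Day 365).
- **Protocol (Amendment 1) 9.1:** efficacy analyses use the stratification factors unless the plan says otherwise.
- **SAP 7.2:** p-values outside the testing sequence are nominal.

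**The concern.** The paragraph merges two questions. One is whether the arms differ in the proportion who have resumed menses by a given day. The other is whether they differ in the timing of resumption over the whole period. The rate differences and their intervals answer the first. The log-rank test answers the second. A reader who sees a Week 76 difference, its interval and a p-value in one row will take the p-value as a test of that difference, and it is not. Elsewhere the SAP keeps the two apart: a fixed-time test for the sustained responder rates and a log-rank test for time to relapse.

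The second, smaller matter is stratification. Section 7.4.2.4 leaves the strata out and then sends the reader, without qualification, to a section that puts them in. A programmer cannot tell whether this is a deliberate exception or a slip.

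**Working it through.** **The plan's own figure.** None exists for this endpoint, and no sample size or power rests on it. The power statement in SAP 2.2 concerns the primary endpoint. It reproduces: 360 × 0.8 / 2 = 144 evaluable per arm, and for 40% against 60% at two-sided 0.05, z = (0.2 × √144 − 1.96 × √0.5) / √(0.24 + 0.24) = 1.46, so power is 92.8%. It has no bearing on this point.

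**Step 1: the hypotheses.** Let S(t) be the probability of not having resumed menses by day t.

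- Log-rank: compares observed with expected events at every event time. Its null is S_R(t) = S_P(t) for all t up to the end of the data.
- Fixed-time log-log test (SAP 7.3.1.1, unstratified form): [log(−log S_R) − log(−log S_P)]² / {V_R/(S_R log S_R)² + V_P/(S_P log S_P)²} at one day. Its null is S_R = S_P at that day only.

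The reported rate difference is zero exactly when S_R = S_P at that day, so only the second test addresses it. One full-curve log-rank gives a single p-value for both weeks. Truncating it at each week gives two p-values, but each still compares the curves up to that week.

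**Step 2: illustration.** Assumptions, none of them from the documents: 60, 90 or 120 patients per arm; censoring of 20% per year; 1,000 runs; nominal 0.05. The Monte Carlo standard error near 5% is √(0.05 × 0.95 / 1000) = 0.7 points.

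- Case A, equal rates but different timing: S at Days 28, 84, 169 and 365 is 0.92, 0.72, 0.40, 0.30 in one arm and 0.70, 0.48, 0.40, 0.30 in the other.
- Case B, identical curves to Day 169 (S = 0.60), then 0.50 against 0.25 at Day 365.
- Case C, identical curves throughout.

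Percentage of runs rejecting, for 60 / 90 / 120 per arm:

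| Case | Log-rank to Day 169 | Log-rank, full | Log-log, Day 169 | Log-log, Day 365 |
|---|---|---|---|---|
| A | 19.6 / 26.0 / 32.7 | 18.1 / 22.6 / 29.5 | 3.5 / 3.9 / 4.3 | 4.2 / 4.5 / 5.2 |
| B | 5.1 / 5.5 / 6.6 | 50.4 / 70.0 / 80.1 | 4.5 / 5.3 / 6.5 | 77.1 / 91.3 / 96.6 |
| C | 5.0 / 5.4 / 5.6 | 4.4 / 5.7 / 4.8 | 4.7 / 4.9 / 5.0 | 4.8 / 5.3 / 4.7 |

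In A, the log-rank test rejects although neither rate differs. In B, the full-curve p-value would stand beside a Week 76 difference of zero, and it is also less sensitive than the fixed-time test to the real Week 104 difference. In C, every test holds its level.

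**Step 3: stratification.** Assumptions: 90 per arm, four equally likely strata, hazard ratio 0.65, with a step in log hazard between adjacent strata.

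| Step | Power, unstratified | Power, stratified | Type I error, unstratified / stratified |
|---|---|---|---|
| 0 | 61.5% | 61.0% | 5.1% / 5.5% |
| 0.4 | 54.6% | 60.8% | 5.9% / 5.8% |
| 0.8 | 38.3% | 59.3% | 4.6% / 4.7% |

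Leaving out the strata does not bias the test. It costs power only when the strata are prognostic.

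**The case against.** The strongest reply is that Section 7.4.2.4 is an endpoint-specific rule which says plainly that the test is unstratified, and the protocol permits such exceptions. A motive is easy to supply. SAP 7.1 already drops region because one of eight strata has fewer than 10 patients, and this endpoint uses only a subset, so its strata are thinner. The pointer to Section 7.1.3 may refer only to its KM method and confidence interval. This stands in part: a reader might infer that the SAP contradicts itself or prescribes an invalid test, and the documents support neither. What remains is an unreconciled cross-reference and a missing reason. Sparse strata are also a weaker motive than they look, because a stratum without events adds nothing to a stratified log-rank test and does not stop its calculation.

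A second reply is that the tests may rarely disagree in practice. With strongly separating assumed curves (90 per arm; 90% against 30%, or 80% against 40%, resuming), the log-rank and the fixed-time tests at both weeks rejected in every run. This also stands. The documents do not suggest that women kept on relugolix catch up with withdrawn women by Day 365.

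For the same reason, a reader should not infer a large false-positive rate. An extreme pair of assumed curves (60% resuming in both arms, one exponential with mean 40 days, the other uniform over 365 days, 90 per arm) gives 47% rejection by log-rank against 6% for a fixed-time comparison at Week 104. But at Day 169 those curves stand at 59% and 28%, a real difference of 31 points, and as a test of timing the log-rank is right to reject. It is a worst case and not an estimate for this trial.

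Finally, the KM rates, differences and intervals are reported whatever p-value is attached, and Protocol 9.3.2.1 plans only a KM description for time-to-event endpoints.

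**Conclusion.** The point holds, at low severity. The p-value named in Section 7.4.2.4 does not test the rate differences it is attached to. That follows from the definition of the two tests and needs no assumption. How often it would mislead does depend on assumptions: 18% to 33% rejection against 3.5% to 5.2% in Case A, and agreement between the tests when the curves separate widely. The unstratified log-rank is a valid test; its possible cost is power, from nothing to about 21 points (59.3% − 38.3%) in the assumed settings.

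The sample size, the primary result and the error control for the primary and key secondary endpoints do not change.

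**What to change.** 1. For the resumption rates at Week 76 and Week 104, take the p-values from the fixed-time log-log test of SAP 7.3.1.1 at Day 169 and Day 365, with its existing stratified-then-unstratified fallback. Word the fallback to cover also a stratum in which every patient has resumed, since log(−log S) is undefined at S = 0 as well as at S = 1.
2. Report one log-rank p-value, labelled as the test of time to resumption. Stratify it by pivotal baseline MBL and prior relugolix exposure as in Section 7.1.3, or keep it unstratified, state the sparse-strata reason, and note the exception in Section 7.1.3.

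The p-value and interval for each rate will then address the same quantity. They need not agree exactly at the margin: in Section 7.3.1.1 the test is on the log-log scale and the interval for the difference is an unstratified linear one. It should not be assumed that a stratum-weighted difference test matching that interval is already specified for the primary endpoint, because it is not.

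The cost is a few lines of SAP text before unblinding and the reuse of a method already specified for the primary endpoint. No data collection changes.

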7.4.2.6. Change and Percent Change from Week 52/Baseline in Hemoglobin

The change and percent change from Week 52/Baseline in hemoglobin during the randomized treatment period will be summarized at each scheduled visit as described in Section 7.1.2.

The change and percent change from Week 52/Baseline in hemoglobin during the cumulative treatment period will be summarized descriptively by visit.

7.4.2.7. Proportion of Patients with Anemia or Below Lower Limit of Normal

The proportion of patients with anemia (hemoglobin values \leq 10.5 g/dL) during the randomized treatment period will be summarized by visit. Similarly, the proportion of patients with hemoglobin values below the lower limit of normal (ie, $<$ 11.6 g/dL) during the randomized treatment period will also be summarized by visit.

The proportion of patients with hemoglobin \leq 10.5 g/dL and with hemoglobin $<$ 11.6 g/dL will also be summarized by visit for the cumulative treatment period.

7.4.2.8. Change from Week 52/Baseline in SF-36v2 Scores

Change from Week 52/Baseline in SF-36v2 scores of eight scales and two summary components during the randomized treatment period will be summarized using descriptive statistics. The scores after the time of retreatment initiation with open-label relugolix + E2/NETA will not be included in the analysis for randomized treatment period.

Change from Week 52/Baseline in SF-36v2 scores of eight scales and two summary components during the cumulative treatment period will be summarized by visit.

Calculation of SF-36v2 Scale Scores

The eight SF-36v2 scales, including Physical Functioning, Role-Physical, Bodily Pain, General Health, Vitality, Social Functioning, Role-Emotional, Mental Health, and Reported Health Transition will be calculated using the PRO CoRE™ Scoring Software provided by QualityMetric Incorporated, LLC. The physical component summary (PCS) and mental component summary (MCS) scores will also be calculated using this software.

PRO CoRE™ is a validated tool that an organization can use to score health-related quality of life data and feel confident that the data was scored correctly. The eight SF-36v2 scales are normalized using mean scores and their SDs from the 2009 general US population, and then they are aggregated using weights from the 2009 general US population to obtain PCS and MCS. Finally, the normalized scores of the eight scales and two component summaries provided by the software will be used for analysis. Higher scores indicate higher health related quality of life.

7.4.2.9. Change from Week 52/Baseline in PGA Score

Change from Week 52/Baseline in PGA for functions and symptoms during the randomized treatment period will be summarized using descriptive statistics. The scores after the time of retreatment initiation with open-label relugolix + E2/NETA will not be included in the analysis for randomized treatment period.

Categorical change from Week 52/Baseline at each visit will also be summarized for randomized treatment period and cumulative treatment period separately. The PGA for function and symptoms will be evaluated using a 5-point response scale (eg, absent, mild, moderate, severe, and very severe). To calculate change from Week 52/Baseline to Week 76 or Week 104, the numerical scores shown in [Table 13](#) will be assigned to each response level.

Table 13: Patient Global Assessment Numerical Scores

Response Scale (Function)	Response Scale (Symptoms)	Numerical Score
No limitation at all	Not severe	1
Mild limitation	Mildly severe	2
Moderate limitation	Moderately severe	3
Quite a bit of limitation	Very severe	4
Extreme limitation	Extremely severe	5

For each item, the count and proportion of improvement by level or at least one level will be tabulated by treatment group and by visit. The denominator for the proportion will be based on the number of patients who provided non-missing responses to the items.

The change from Week 52/Baseline in PGA scores during the cumulative treatment period will be summarized descriptively by visit.

7.4.2.10. Change from Week 52/Baseline in the WPAI-UF Scores

Change from Week 52/Baseline in WPAI-UF scores during the randomized treatment period will be summarized using descriptive statistics. The scores after the time of retreatment initiation with open-label relugolix + E2/NETA will not be included in the analysis for randomized treatment period.

Change from Week 52/Baseline in WPAI-UF scores during the cumulative treatment period will be summarized by visit.

Calculation of WPAI-UF Scores

WPAI-UF outcomes are expressed as impairment percentages, with higher numbers indicating greater impairment and less productivity, ie, worse outcomes. There are six questions in this questionnaire:

1 = currently employed

2 = hours missed due to uterine fibroid symptoms

3 = hours missed other reasons

4 = hours actually worked

5 = degree uterine fibroid symptoms affected productivity while working in past 7 days

6 = degree uterine fibroid symptoms affected regular activities in past 7 days

If a patient is not employed (ie, answered no to the first question), only question 6 needs to be answered.

Four WPAI-UF scores will be calculated using the following algorithms (Reilly et al. 1993; Reilly Associates Health Outcomes Research website [<http://www.reillyassociates.net>]) and analyzed. Multiply the scores by 100% to express them in percentages. Higher percentages indicate that impairment due to Uterine Fibroids is worse.

- Percent work time missed due to uterine fibroid symptoms: $Q2/(Q2 + Q4) \times 100\%$
- Percent impairment while working due to uterine fibroid symptoms: $Q5/10 \times 100\%$
- Percent overall work impairment due to uterine fibroid symptoms:
 $\{Q2/(Q2 + Q4) + [1 - Q2/(Q2 + Q4)] \times (Q5/10)\} \times 100\%$
- Percent activity impairment due to uterine fibroid symptoms: $Q6/10 \times 100\%$

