Appendix 3. Work Productivity Activity Impairment -Uterine Fibroids (WPAI-UF)

Work Productivity and Activity Impairment Questionnaire: Uterine Fibroids V2.0 (WPAI:UF)
The following questions ask about the effect of uterine fibroid symptoms on your ability to work and perform regular activities. Please fill in the blanks or circle a number, as indicated.
Are you currently employed (working for pay)? If NO, check "NO" and skip to question 6. YES
The next questions are about the past seven days , not including today.
 During the past seven days, how many hours did you miss from work because of problems associated with your uterine fibroid symptoms? Include hours you missed on sick days, times you went in late, left early, etc., because of your uterine fibroid symptoms. Do not include time you missed to participate in this study.
HOURS
3. During the past seven days, how many hours did you miss from work because of any other reason, such as vacation, holidays, time off to participate in this study?
HOURS
4. During the past seven days, how many hours did you actually work?
HOURS (If "0", skip to question 6.)
English for USA – WPAI:UF V2.0 – 10/FEB/2016

Effective: 13-August-2018

During the past seven days, how much did your uterine fibroid symptoms affect your productivity while you were working?

Think about days you were limited in the amount or kind of work you could do, days you accomplished less than you would like, or days you could not do your work as carefully as usual. If uterine fibroid symptoms affected your work only a little, choose a low number. Choose a high number if uterine fibroid symptoms affected your work a great deal.

Consider only how much uterine fibroid symptoms affected productivity while you were working.

+‡+			Р	ouu	LUVILY	VVIII	ie yu	u we	SIC W	OIKII	М-		
	Uterine fibroid symptoms had no effect on my work	0	1	2	3	4	5	6	7	8	9	10	Uterine fibroid symptoms completely prevented me from working
					CIE	CLE	ΑΝ	UMF	RFR				

6. During the past seven days, how much did your uterine fibroid symptoms affect your ability to do your regular daily activities, other than work at a job?

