4. GENERAL CONSIDERATIONS FOR DATA ANALYSES AND HANDLING OF MISSING DATA

4.1. Data Presentation Conventions

All statistical analyses will be conducted using SAS[®] Version 9.2 or higher.

All confidence intervals (CIs) will be reported as two-sided unless otherwise stated.

Where appropriate, variables will be summarized descriptively by study visit. For the categorical variables, the count and proportions of each possible value will be tabulated by treatment group. For continuous variables, the number of patients with non-missing values, mean, median, standard deviation (SD), minimum, and maximum values will be tabulated.

Unless otherwise specified, the following conventions will be applied to all analyses:

- Mean and median values will be formatted to one more decimal place than the measured value. Standard deviation values will be formatted to two more decimal places than the measured value. Minimum and maximum values will be presented to the same number of decimal places as the measured value. If the measured value is large (eg, > 100), fewer decimal places may be displayed.
- Percentages will be rounded to one decimal place;
- p-values will be rounded to four decimal places. p-values < 0.0001 will be presented as “< 0.0001” and p-values > 0.9999 will be presented as “> 0.9999”;
- 1 month = 30.4375 days. Month is calculated as (days/30.4375) rounded to one decimal place;
- 1 year = 365.25 days. Year is calculated as (days/365.25) rounded to one decimal place;
- Age will be calculated using the date of randomization. If only year of birth is collected, 1 July of the year of birth will be used to calculate age.
- 1 pound = 0.454 kg;
- 1 inch = 2.54 cm;
- Missing efficacy or safety data will not be imputed, unless otherwise specified;
- For laboratory results above or below sensitivity limits displayed as “<” or “>,” a quantification threshold, 0.000000001, will be subtracted or added, respectively, to the threshold to derive a numeric result for analyses;
- For MBL volume reported as below the limit of quantification (eg, MBL below Quantification Level < 5.0 mL or < 2.5 mL), 0.000000001 will be subtracted from the reported quantification threshold for the visit to derive a numeric result for analyses;
- For safety analyses, calculation of percentages will be calculated on the basis of the number of patients in the analysis population in each treatment group;

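### The WPAI-UF overall work impairment score comes out missing, instead of 100%, for an employed woman who lost hours to fibroid symptoms and worked none

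*SAP*

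**What the plan says.** SAP 7.4.2.10 derives four WPAI-UF scores, on which higher percentages are worse. The one at issue, "Percent overall work impairment due to uterine fibroid symptoms", is

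{Q2/(Q2 + Q4) + [1 - Q2/(Q2 + Q4)] x (Q5/10)} x 100%.

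The SAP labels its inputs as follows:

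- "2 = hours missed due to uterine fibroid symptoms"
- "4 = hours actually worked"
- "5 = degree uterine fibroid symptoms affected productivity while working in past 7 days"

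In Protocol Appendix 3, the answer line for question 4 tells a woman who enters zero hours to "skip to question 6". Q5 is therefore blank by design for anyone who did no work in the seven-day recall period. The same direction also follows question 1, for women who are not employed.

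The SAP deals only with the second group: "If a patient is not employed (ie, answered no to the first question), only question 6 needs to be answered". It does not mention an employed woman with Q4 = 0. Its general rule, in SAP 4.1, is "Missing efficacy or safety data will not be imputed, unless otherwise specified", and SAP 4.4.1 limits by-visit analyses to observed records. The only missing-item rule for a questionnaire is in SAP 7.4.2.11, and it covers the UFS-QoL.

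**The concern.** The formula needs an item that the questionnaire withholds when no hours were worked. The score is then lost because of its own value: the woman did not work, at least partly because of her fibroids, and that is the worst state the score can record. She would appear as 100% in percent work time missed and as missing in overall work impairment at the same visit.

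The arm mean for overall impairment would be too low. If such weeks were more frequent in one arm, the comparison between arms would also be distorted. There is a reproducibility problem as well. One programmer may code the printed expression as it stands, and another may notice the zero weight and enter 100%. Both could say that they had followed the SAP.

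**Working it through.** **Inputs.** The formula is from SAP 7.4.2.10, the skip from Protocol Appendix 3, and the no-imputation rule and the software (SAS) from SAP 4.1. The plan states no WPAI-UF figure to reproduce.

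**Step 1: the case at issue.** Take Q2 = 40, Q4 = 0, Q5 blank.

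- Percent work time missed: 40/(40 + 0) = 100%.
- Weight on Q5/10: 1 - 40/40 = 0.
- Overall impairment as printed: 1 + 0 x missing. In SAS arithmetic this is missing.

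**Step 2: what the score should be.** With weight zero, every Q5 from 0 to 10 gives 1 + 0 x (Q5/10) = 100%. The blank item carries no information. The number of hours lost does not matter either: Q2 = 8, Q4 = 0 also gives 100%. Hours missed for other reasons (Q3) do not enter the formula.

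**Step 3: who else is affected.**

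| Q2 | Q4 | Q5 | As printed | With an explicit rule |
|---|---|---|---|---|
| 40 | 0 | blank | missing | 100% |
| 8 | 0 | blank | missing | 100% |
| 39 | 1 | 5 | 98.75% | 98.75% |
| 39 | 1 | 10 | 100% | 100% |
| 20 | 20 | 10 | 100% | 100% |
| 0 | 40 | 10 | 100% | 100% |
| 0 | 0 | blank | 0/0 | not calculated |

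The loss is confined to Q2 > 0 with Q4 = 0. No score with Q4 > 0 changes. The 0/0 row is a second case that the SAP leaves open.

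**Step 4: effect on an arm mean.** Let f be the share of employed women at a visit with Q2 > 0 and Q4 = 0, and m the mean of the others. With these women kept, the mean is 100f + (1 - f)m. Without them it is m. The understatement is f x (100 - m). Both f and m are assumptions:

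| f | m = 10% | m = 20% | m = 30% |
|---|---|---|---|
| 1% | 0.9 | 0.8 | 0.7 |
| 3% | 2.7 | 2.4 | 2.1 |
| 5% | 4.5 | 4.0 | 3.5 |

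These are points on the mean score at a visit. For the mean change from Week 52/Baseline, the shift is f x (change in the lost women - mean change in the others). A woman whose baseline week is the affected one loses every change value.

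**Step 5: effect on the difference between arms.** If the others average 20% in both arms, the error in placebo minus relugolix is 80 x (f_placebo - f_relugolix), which is zero when the shares are equal. If the shares are equal but the others' means differ, a small term f x (difference in means) remains. For f = 3% and means of 30% and 20% it is 0.03 x 10 = 0.3 points, and it enlarges the observed difference.

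**The case against.** The strongest reply is that the formula is coherent. With Q4 = 0 and Q2 > 0 the Q5 term vanishes, so entering 100% is a derivation, not an imputation, and the no-imputation rule does not forbid it. SAP 7.4.2.10 also cites the instrument's publication and the developer's website, which may contain a rule for zero hours worked. Those sources are outside the documents, so nothing can be said about their content. What stands is that the SAP prints its own algorithms, that they contain no such rule, and that literal coding returns missing. The SAP should not depend on a programmer noticing the zero weight.

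A reader might infer that the worst scores as a class drop out. They do not: women who worked some hours and rated Q5 as 10 keep their 100%.

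A reader might also infer that the treatment comparison is biased towards no effect, because bleeding returns on placebo. The documents do not support this as a finding. Under SAP 2.1 a woman who relapses is offered open-label drug at her next menses, and SAP 7.4.2.10 excludes scores after retreatment starts from the randomized-period analysis. The visits most exposed are those between relapse and retreatment. The numbers are small too. With 180 per arm and 70% employed (assumed), there are 126 women, so f = 1% to 3% is about 1 to 4 women. On the SAP 2.2 assumption of 40% placebo responders, about 72 placebo women would be relapse-free at Week 76. At 70% employed that is about 50, or 0.5 to 1.5 women, before dropout.

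Finally, an affected woman still counts as 100% in percent work time missed, and she still answers Q6, so her impairment does not disappear from the WPAI-UF results.

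**Conclusion.** Wrong as written, minor. For an employed woman with Q2 > 0 and Q4 = 0, the printed formula gives a missing overall work impairment score when the data collected fix it at 100%. This follows from the documents and from SAS arithmetic, and needs no assumption about the trial's data.

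The size does rest on assumptions. With the others averaging 20%, the arm mean is understated by 0.8 points at f = 1% and 2.4 points at f = 3%. If the others' mean is the same in both arms, the difference is biased only when f differs between them. That is plausible for placebo visits between relapse and retreatment, but it is not shown.

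The consequence is limited. WPAI-UF is an other secondary endpoint, and 7.4.2.10 plans descriptive statistics for it. SAP 7.4 opens with a general promise of comparative statistics for secondary endpoints, but the score is outside the fixed testing sequence in SAP 7.4.1 either way. No primary or key secondary conclusion depends on it.

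**What to change.** Add to SAP 7.4.2.10: if Q2 > 0 and Q4 = 0, overall work impairment is 100%, and percent impairment while working stays missing because no work was done; if Q2 + Q4 = 0, percent work time missed and overall work impairment are not calculated.

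The cost is one sentence in the SAP and a line of code. No score with Q4 > 0 changes and no new data are needed. Reporting the number of women with Q2 > 0 and Q4 = 0 by arm and visit would also replace the assumed f with the observed one.
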